#### 2.2 Study Objectives

#### 2.2.1 Safety Objective

To assess the safety and tolerability of escalating doses of IV ganaxolone as determined by AEs and changes from baseline in laboratory measures, vital signs, Columbia Suicide Severity Rating Scale (CSSRS), electrocardiogram (ECG), Stanford Sleepiness Scale (SSS), and physical examination. In Cohort 6 the safety of IV dosing followed by oral dosing is investigated using the same assessments as in Cohorts 1-5.

#### 2.2.2 Efficacy Objective

To explore the efficacy of escalating doses of IV ganaxolone in the treatment of PPD with the 17-item Hamilton Depression Rating Scale (HAMD17), Edinburgh Postnatal Depression Scale (EPDS), Spielberger State-Trait Anxiety Inventory six item version (STAI6) and Clinical Global Impression-Improvement (CGI-I) scale. In Cohort 6 the efficacy of IV dosing followed by oral dosing is explored using the same assessments as in Cohorts 1-5.

#### 2.2.3 **Pharmacokinetic Objective**

To collect samples of blood for pharmacokinetic analysis to assess ganaxolone plasma exposure after administration of intravenous and oral ganaxolone.

#### **3.0 STUDY DESIGN**

#### 3.1 Study Design and Study Population

This is a Phase 2A, double-blind, placebo-controlled, multiple-dose escalation study consisting of up to 6 cohorts (Cohorts 1-6).

Approximately 200 women with PPD 18–45 years of age will be screened to randomize up to 100 subjects across up to 6 cohorts. Approximately 10-30 subjects will be randomized into each cohort.

In Cohorts 1-5, the treatment is administered intravenously over 60 hours. Randomized subjects will receive IV ganaxolone or matching IV placebo in a 1:1 ratio. More specifically, the dosing for Cohorts 1-5 is as follows:

**Cohort 1:** ganaxolone is infused at a rate of 4 mg/h (16 ml/h of ganaxolone 0.25 mg/ml solution) for 48 hours and then at a rate of 2 mg/h for the next 12 hours. The infusion is stopped at 60 hours.

**Cohort 2:** ganaxolone is infused at a rate of 8 mg/h (16 ml/h of ganaxolone 0.5 mg/ml solution) for 48 hours and then at a rate of 4 mg/h for the next 12 hours. The infusion is stopped at 60 hours.

**Cohort 3:** Twelve mg bolus of ganaxolone is initially given over 2 minutes followed by ganaxolone infusion at a rate of 12 mg/h (24 ml/h of ganaxolone 0.5 mg/ml solution) for 48 hours. The rate is then reduced to 6 mg/h for the next 12 hours. The infusion is stopped at 60 hours.

**Cohorts 4 and 5:** Cohorts 4 and 5 are optional and will be utilized only if further dose exploration is warranted. Ganaxolone infusion rate will be decided based on the results of Cohorts 1-3. However, the initial bolus dose will not exceed 16 mg over 2 minutes and the maximum infusion rate will not exceed 16 mg/h.

**In Cohort 6**, subjects randomized to ganaxolone will receive an initial IV infusion of 20 mg/h (40 ml/h of ganaxolone 0.5 mg/ml solution) for 6 hours followed by 900 mg (4 capsules) ganaxolone capsules administered orally at dinner time for 28 days followed by a 3-day taper (3, 2, and 1 capsules per day, respectively). Subjects randomized to placebo will receive an initial IV infusion of matching placebo (at 40 ml/h) followed by 4 placebo capsules administered orally at dinner time for 28 days followed by a 3-day taper (3, 2, and 1 capsules per day, respectively). Randomization will allocate subjects to the ganaxolone arm or placebo arm in 1:1 ratio.

#### 3.2 Rationale for Study Design

Rapid changes in allopregnanolone and other neurosteroid levels during and after pregnancy are thought to contribute to the biological underpinnings of PPD. There are also data suggesting that

the sensitivity of the GABA system is altered during pregnancy and after childbirth, possibly as a result of changes in the circulating neurosteroid levels, and that there may be a state of neurosteroid withdrawal after pregnancy. Ganaxolone may alleviate PPD by increasing neurosteroid activity.

Although ganaxolone has been administered to more than 1,500 subjects there have been no prior studies establishing the safety or efficacy of ganaxolone in clinical studies of PPD or other mood disorders in women. This study is designed to establish the safety profile of intravenous ganaxolone in women with PPD. The safety of transition from IV treatment to oral treatment is investigated in Cohort 6. Potential efficacy signals will also be explored. These data will be used to select a dose (or doses) and dosing regimen for further development of ganaxolone in PPD.

#### 3.3 Blinding Scheme

Within cohorts, subjects will be randomized to ganaxolone or placebo in a 1:1 ratio. The randomization scheme will be prepared by an independent third-party vendor. Treatment assignments will be obtained by the investigator (or designee) via an Interactive Voice and/or Web Response System (IxRS). Subjects who are randomized to receive ganaxolone in Cohorts 1-5 will receive ganaxolone as an intravenous infusion for 60 hours with or without an intravenous ganaxolone bolus dose. Subjects who are randomized to placebo will receive matching placebo infusion for 60 hours (0.9% saline) with or without a matching intravenous placebo bolus dose. The placebo infusion is identical to ganaxolone in its appearance. In Cohort 6, subjects randomized to ganaxolone will receive an initial infusion of 20 mg/h (40 ml/h of ganaxolone 0.5 mg/ml solution) for 6 hours followed by treatment with oral doses of 900 mg ganaxolone (4 capsules per dose) for 28 days followed by a 3-day taper (3, 2, and 1 capsules per day, respectively). Subjects randomized to placebo will receive an initial infusion with matching IV placebo (at 40 ml/hr) followed by matching oral placebo (4 capsules per dose) for 28 days followed by a 3-day taper (3, 2, and 1 capsules per day, respectively). The placebo infusion and placebo capsules are identical to the ganaxolone infusion and ganaxolone capsules, respectively, in their appearance. An unblinded study pharmacist at the investigative site will prepare the ganaxolone and placebo IV solutions and allocate capsule supply for Cohort 6. Members of the DRC will be unblinded at scheduled DRC meetings. All other study personnel, including persons involved in the evaluation of the study subjects (e.g. investigators, sub-investigators, and physicians/nurses), will remain blinded at all times, except in case of an emergency. Subjects will be blinded.

#### 3.4 Dose Selection

#### 3.4.1 **Cohort 1**

For Cohort 1, the targeted ganaxolone plasma concentration at steady state ( $C_{ss}$ ) will be 52 ng/ml, which is estimated to be achieved with a ganaxolone infusion rate of 4 mg/hr (16 ml/h of ganaxolone 0.25 mg/ml solution). Steady state is expected to be achieved within 24 hours.

For Cohort 1, the infusion rate is lowered to 2 mg/h after + 48 hours of infusion and stopped at + 60 hours. This is done to minimize any risks for withdrawal or rebound of anxiety and depression symptoms.

The target ganaxolone exposure level of approximately 52 ng/ml for Cohort 1 was chosen to achieve a level similar to that of allopregnanolone at the end of pregnancy. Allopregnanolone levels increase gradually throughout pregnancy reaching a peak mean concentration at the end of pregnancy of about 15 to 60 ng/ml. The levels then drop precipitously after the delivery. We hypothesize that substitution of the low allopregnanolone levels with ganaxolone would alleviate or reverse the symptoms of PPD.

#### 3.4.2 **Cohort 2**

For Cohort 2, the ganaxolone infusion rate will be 8 mg/hr (16 ml/h of ganaxolone 0.5 mg/ml solution). The infusion rate will be lowered to 4 mg/h (8 ml/h of ganaxolone 0.5 mg/ml solution) after + 48 hours of infusion and will be stopped at + 60 hours. This is done to minimize any risks for withdrawal or rebound of anxiety and depression symptoms. This dose will approximately double the expected plasma exposure as compared to Cohort 1 at steady state (Cohort 2 expected plasma concentration  $\sim$  100-120 ng/mL).

#### 3.4.3 **Cohort 3**

For Cohort 3, an initial 12 mg bolus of ganaxolone will be given over 2 minutes, followed by ganaxolone infusion at a rate of 12 mg/h (24 ml/h of ganaxolone 0.5 mg/ml solution) for 48 hours. The rate will be reduced to 6 mg/h for the next 12 hours, which is done to minimize any risks for withdrawal or rebound of anxiety and depression symptoms. The infusion is stopped at 60 hours.

This dose will increase the expected maximum plasma exposure by about 1.5-fold as compared to Cohort 2 at steady state during the infusion. The expected maximum plasma concentrations will be  $\sim 180$  ng/ml during the infusion. During the initial 2-minute ganaxolone bolus, the peak plasma concentrations are expected to increase up to 300 ng/ml transiently, and then falling rapidly below 100 ng/ml after the bolus dose has been completed.

The bolus dose is justified to provide a rapid loading dose of ganaxolone, which is hypothesized to expedite the onset of antidepressant activity.

Based on prior studies with the oral formulation and results from Phase 1 Study 1042-0405 in healthy volunteers using the IV formulation of ganaxolone, the Cohort 3 dose and associated plasma exposure is expected to be generally safe and well tolerated.

#### 3.4.4 **Cohorts 4 and 5**

Cohorts 4 and 5 are optional and will be utilized only if further dose exploration is warranted. Ganaxolone infusion rate will be decided based on the results from previous cohorts. However, no bolus doses higher than 16 mg over 2 minutes will be administered. The cap for the maximum infusion rate in Cohorts 4 and 5 will be 16 mg/h (not including any ganaxolone given by bolus). Ganaxolone was administered to healthy volunteers in Study 1042-0405 at these dose levels and above without any safety concerns (see below for details). With this maximum bolus and infusion rate the amount of Captisol® infused over 24 hours will not exceed the maximum levels achieved with Carnexiv®, an approved IV carbamazepine product.

#### 3.4.5 **Cohort 6**

For Cohort 6, the goal of initiation of treatment with IV infusion followed by oral capsules is to maximize the speed of onset of antidepressant activity while providing the convenience of oral dosing for the remainder of the treatment period. Under this IV-oral dosing schedule there may not be a need for a prolonged inpatient observation.

This initial infusion is targeted to provide a fast onset of antidepressant activity by delivery of rapid plasma exposures to ganaxolone. At dinner time of Day 1 the subjects will take their first oral dose of ganaxolone 900 mg or matching placebo (4 capsules). This dose is expected to provide mean  $C_{max}$  plasma concentrations of approximately 250-300 ng/mL and mean steady-state levels between 90 and 150 ng/mL, which may be mildly sedating. In previous studies ganaxolone has been given up to a daily dose of 2000 mg, and at single doses of 1000 mg. Based on the previous experience this dose is expected to be safe.

At subsequent nights (Days 2-28), the target dose is ganaxolone 900 mg or matching placebo (4 capsules) at dinner time followed by a 3-day taper (3, 2, and 1 capsule/s per day, respectively). However, based on the assessment of the investigator the dose may be maintained at 675 mg or 450 mg (or matching placebo) in case of adverse events, such as grogginess in the morning. In the case of 3 capsules per day on day 28 the taper will consist of 2, 2, and 1 capsule/s on days 29, 30, and 31, respectively. In the case of 2 capsules per day on day 28 the taper will consist of 1 capsule on days 29, 30, and 31. If the subject cannot tolerate 450 mg (or matching placebo) per dose the investigator will contact the Medical Monitor to discuss dosing options.

Subjects will be provided with a diary to capture the details of dose administration and associated food intake throughout the treatment period. Subjects will document the number of capsules taken and whether a fatty meal/snack (e.g., fatty yogurt, nuts, avocado) was consumed  $\pm 15$  minutes of taking the capsules.

The mechanism by which ganaxolone is postulated to be efficacious under this dosing regimen is restructuring of sleep architecture. Preclinical studies have shown that allopregnanolone has the capacity to modulate sleep, and disturbed sleep architecture is one of the hallmarks of depression.

#### 3.4.6 **Dose justification in context of previous experience with IV ganaxolone**

In Study 1042-0405, which was a Phase 1 study in healthy volunteers investigating the safety of IV ganaxolone, infusion of 30 mg/h for 1 hour, 20 mg over 2 minutes and 20 mg/h for 4 hours led to peak concentrations of 258, 441 and 215 ng/mL, respectively, without any safety concerns. Sedation was assessed using the Modified Observers Assessment of Alertness/Sedation (MOAAS) scale. On this scale, score 5 indicates no sedation (responds readily to name spoken in normal tone) while score 1 indicates deep sedation (responds only after painful trapezius squeeze). In these cohorts, vast majority of the scores were 5 with few exceptions of 4 (lethargic response to name spoken in normal tone) and 3 (responds only after name is called loudly or repeatedly). The sedation scores reversed quickly after the infusion was stopped. The highest bolus dose tested was 30 mg, which was infused over 5-minutes. This dose led to peak concentration levels ( $C_{max}$ ) of > 1,000 ng/mL with no safety concerns (except sedation).

Six subjects reported treatment emergent AEs. No single AE was seen twice. Only one event, headache, was considered by the investigator to be related to ganaxolone. None of the treatment emergent AEs was serious, and all were of mild intensity. No clinically meaningful mean changes in laboratory test results, vital signs, or ECG parameters occurred in any cohort.

This safety profile is consistent with findings from previous studies with the oral formulation of ganaxolone, in which  $C_{max}$  levels of up to 200 to 300 ng/mL were commonly observed and were not associated with major safety findings or toxicity (apart from sedation-related effects).

#### 3.5 Justification for Placebo as a Control Group

There are no approved treatments for PPD although SSRIs and serotonin and norepinephrine reuptake inhibitors (SNRIs) are commonly used off-label to manage PPD. All subjects whether randomized to the placebo or control group will be allowed to remain on their current antidepressants provided that they have not had a recent change in the medication regimen (for details, please see Section 5.3.2 for prohibited treatments). The add-on design minimizes subject risks because the current medications are not withdrawn, since that could exacerbate depressive symptoms. The duration of the double-blind treatment phase in Cohorts 1-5 of the study is short (60 hours) and is conducted in an inpatient setting, which further minimizes risks to the subjects. The Cohort 6 treatment period is initiated in an inpatient setting, which allows observation of the effects of the IV infusion and first dose effects of the oral medication during the approximately 48-hour stay on the unit.

#### 3.6 Study Duration

The screening period for each cohort will be up to 2 weeks. In Cohorts 1-5 the screening period is followed by a 60-hour infusion treatment with or without initial bolus dosing during the 4-day inpatient treatment phase at a hospital or clinical pharmacology unit. The subjects will be discharged from the unit on the morning of Day-4. There will be 2 safety follow-up visits after inpatient discharge on post-treatment Weeks 1 and 4. The total duration of the study will be up to 7 weeks for Cohorts 1-5. For Cohort 6 there will be an initial infusion treatment and oral dose during the approximately 24-hour inpatient dosing phase followed by 27 days of oral treatment as outpatient. There will be 3 safety follow-up visits after the outpatient treatment period on post-treatment Weeks 1,4, and 6. The total duration of the study will be up to 12 weeks for subjects participating in Cohort 6.

#### **3.7** Interim Analyses

The study team physician and the clinical operations lead will monitor emerging **blinded** safety data from each subject periodically throughout the duration of the study.

In addition, safety and efficacy data from each cohort will be unblinded, and analyses will be conducted for the purpose of dose selection for the next cohort. The dose for the next cohort will be decided based on these interim data analyses. The decision how to adjust the dose and/or the duration of the infusion will be made based on recommendations by a Data Review Committee (DRC) composed of the sponsor's Chief Medical Officer, and at least 2 other external physicians. At least one of the members will have special expertise in the clinical care of women with depression or postpartum depression. One of the members will have expertise in the

conduct of clinical trials or analysis of clinical trial data. The study team and all parties other than the DRC will remain blinded.

The dose for the subsequent cohorts will be selected with the goal of gaining additional information on ganaxolone's tolerability and dose-response profile.

A separate DRC guidance document outlines the principles for dose selection. Marinus may decide to stop the study, or make the data public, after completion of any cohort.

#### **3.8** Definition of Completion

A cohort is considered complete when the final subject in the cohort has completed the final protocol-defined assessment, including follow-up visits, for the cohort.

The Study Completion Date is defined as the date the final subject, across all sites, completes her final protocol-defined assessment, including follow-up visits, for the final cohort.

#### **3.9** Sites and Regions

The study will be conducted in the United States at approximately 20 investigative sites.

#### 4.0 STUDY POPULATION

Each subject must participate in the informed consent process and provide written informed consent before any procedures specified in the protocol are performed.

#### 4.1 Inclusion Criteria

The subject will not be considered eligible for the study without meeting all of the criteria below.

- 1. An understanding of and ability, and willingness to fully comply with study procedures and restrictions.
- 2. Ability to voluntarily provide written, signed, and dated informed consent as applicable to participate in the study.
- 3. Female aged 18 to 45 years, inclusive, at the Screening Visit
- 4. Experiencing a Major Depressive Episode, which started between the start of the third trimester and 4 weeks following delivery. The Major Depressive Episode must be diagnosed according to MINI 7.0 interview
- 5. Given birth in the last 12 months
- 6. HAMD17 score of  $\geq$  26 at screening (HAMD17 must be  $\geq$  22 per CTNI rating at Admission to the Unit on Day 0)
- 7. The diagnosis of PPD and severity of depression must be supported by the SAFER interview
- 8. Must agree to stop breastfeeding from start of study treatment to 45 days after end of study treatment
- 9. Must agree to use acceptable contraceptive methods during the study period

#### 4.2 Exclusion Criteria

Subjects are excluded from the study if any of the following exclusion criteria are met:

- 1. Current or past history of any psychotic illness, including Major Depressive Episode with psychotic features
- 2. Any psychiatric condition that, in the investigator's judgment, is considered clinically significant and could affect subject safety or study outcome including eating disorder, panic disorder, obsessive-compulsive disorder, or post-traumatic stress disorder
- 3. History of suicide attempt within the past 3 years (actual attempt, interrupted or aborted attempt, preparatory acts, or behavior)
- 4. Active suicidal ideation (e.g. answering "yes" to questions 4 or 5 in the CSSRS suicidal ideation section)
- 5. History of severe bipolar I disorder (e.g. hospitalization due to the illness, lifetime history of psychosis or suicide attempt)

- 6. Uncontrolled seizure disorder
- 7. Current or history within the past 3 years of any substance use disorder, with the exception of tobacco or caffeine
- 8. Positive drug screen for any illicit substances or prescription drugs at screening or randomization. If the drug screen is positive for a prescription drug that has the potential to be abused (e.g. amphetamine, benzodiazepine), legitimate use of the drug must be verified by the subject's providing the current pill bottle, prescription for the drug, or a note from the prescribing physician. Cannabis use is prohibited and subjects with positive drug screen for cannabis are excluded. However, occasional users of cannabis may be re-tested if the subject is willing to refrain from consuming cannabis-based products during the trial. If the re-test sample is negative at screening the subject can be considered eligible. If the re-test sample is positive for cannabis the investigator may ask for determination of the urine or blood levels of Δ9-tetrahydrocannabinol (THC), and its metabolites 11-hydroxy-THC and, 9-carboxy-THC. If the levels of THC are not detectable the subject may be considered eligible for the trial.
- 9. Current or relevant history of any medical disorder that may require treatment or make the subject unlikely to be able to complete the study, or any condition that presents undue risk from the investigational product or procedure point of view
- 10. Any clinically significant abnormality identified on physical examination, ECG or laboratory tests, that in the judgment of the investigator would compromise the subject's safety or successful participation in the clinical study
- 11. Subject has untreated or uncontrolled hypothyroidism
- 12. Known or suspected intolerance or hypersensitivity to the investigational product(s) or allopregnanolone, or any of the stated ingredients
- 13. Use of another investigational product within 60 days prior to the first dose of investigational product
- 14. Has alanine transferase (ALT) or aspartate transferase (AST) greater than 2.5 times upper limit of normal or total bilirubin greater than 1.5 times upper limit of normal (unless elevation is due to Gilbert's syndrome)
- 15. Screening QTcF > 470 msec
- 16. Unwillingness to withhold grapefruit, Seville oranges, star fruit, or citrus derived products from diet between screening and discharge from the study unit
- 17. Receiving concomitant treatment with strong CYP3A4 inducers or strong CYP3A4 inhibitors
- 18. Body mass index  $(BMI) \ge 40$
- 19. Subject is pregnant
- 20. Subject is using prohibited medications as specified in Section 5.3.2

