#### 5.3.2 **Prohibited Treatments**

The following classes of medications and treatments are prohibited during the study treatment period. If the subject has been taking any of these medications before enrollment, there should be a medication-free period of a minimum of 5 days or 5 half-lives of that medication, whichever is longer, before admission to the unit. In general, subjects who require extensive washouts may not be candidates for participation and those cases should be discussed with the medical monitor.

- Benzodiazepines and barbiturates
- Gabapentin and pregabalin
- Anticonvulsants and mood stabilizers
- All hypnotics and sleep aids (with the exception of low-dose diphenhydramine, doxepin, and trazodone as described above)
- Opioids

- Cannabis
- Electroconvulsive Therapy (ECT), rapid transcranial magnetic stimulation (rTMS), vagal nerve stimulation
- Experimental (including hormonal and herbal) treatments of postpartum depression
- Strong inhibitors and inducers of CYP3A4 (Appendix 1)

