### Urine analysis including pregnancy test and urine drug screen

Leukocytes, nitrites, protein, blood, specific gravity, glucose, ketones, urine pregnancy test, urine drug screen (cannabis, opioids [including oxycodone, methadone and buprenorphine], cocaine, benzodiazepines, barbiturates, alcohol [ethanol], and phencyclidine).

Confirmatory testing of positive drug screen findings using for example gas chromatography mass spectroscopy (GCMS) may be conducted.

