#### 7.2.2 Laboratory Measures

Laboratory measures will be assessed at Screening, Day 0, +48h, and Day 11 for the IV only cohorts and at Screening and Days 0, 8, 15, 29, and 57 for the IV to oral cohort. Urine pregnancy tests and drug screens will be conducted at Screening, Day 0, +72h, and Days 11 and 34 for the IV only cohorts and at Screening and at Days 0, 8, 15, 22, 29, 36, 57, and 71. The Day 0 assessment will be the Baseline observation. Neurosteroid levels and PK data will be analyzed separately by other third-party vendors and thus will not be described in this SAP. Per protocol, the following assessments will be done.

• Chemistry: Sodium, potassium, glucose, chloride, carbon dioxide, creatinine, total protein, blood urea nitrogen, albumin, total bilirubin (with reflex fractionation to direct and indirect bilirubin if total bilirubin is elevated and outside of the normal range), alanine aminotransferase, aspartate transferase, alkaline phosphatase, thyroid stimulating hormone (with reflex to free T4 if thyroid

stimulating hormone (TSH) is outside of the normal range),  $\beta$ -HCG (Human Chorionic Gonadotropin)

- Hematology: Hematocrit, hemoglobin, red blood cell count, mean corpuscular volume, mean corpuscular hemoglobin, mean corpuscular hemoglobin concentration, platelet count, white blood cell count with differential
- Urinalysis: Leukocytes, nitrites, protein, blood, specific gravity, glucose, ketones
- Urine Drug Screen: Cannabis, oxycodone, methadone, buprenorphine, cocaine, benzodiazepines, barbiturates, alcohol (ethanol) and phencyclidine

Urine pregnancy results will only be provided in a data listing.

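### Exclusion 8 relies on the urine screen to find amphetamine, which the panel does not test; its prescription check also lacks a link to section 5.3.2 and exclusion 20

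*Protocol*

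**What the plan says.** Criterion 8 appears in the same terms in the protocol synopsis and in section 4.2. Its trigger is "Positive drug screen for any illicit substances or prescription drugs at screening or randomization". It then deals with prescribed drugs: "If the drug screen is positive for a prescription drug that has the potential to be abused (e.g. amphetamine, benzodiazepine), legitimate use" has to be shown. The means of showing it are "legitimate use of the drug must be verified by the subject's providing the current pill bottle, prescription for the drug" or a note from the prescriber. Cannabis has its own re-test rule within the same criterion.

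The screen itself is defined in Protocol 7.8.5.2, under the urine analysis heading, as "urine drug screen (cannabis, opioids [including oxycodone, methadone and buprenorphine], cocaine, benzodiazepines, barbiturates, alcohol [ethanol], and phencyclidine", and the list closes there. SAP 7.2.2 gives "Cannabis, oxycodone, methadone, buprenorphine, cocaine, benzodiazepines, barbiturates, alcohol (ethanol) and phencyclidine". On follow-up of a positive result, the protocol adds only this: "Confirmatory testing of positive drug screen findings using for example gas chromatography mass spectroscopy (GCMS) may be conducted".

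Protocol 5.3.2 prohibits, among other things, "Benzodiazepines and barbiturates" and, as separate entries, opioids and cannabis. For women who had been taking a listed drug it asks for "a medication-free period of a minimum of 5 days or 5 half-lives of that medication, whichever is longer, before admission to the unit". Exclusion 20 in section 4.2 excludes anyone using a 5.3.2 drug and contains no allowance for a valid prescription.

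**The concern.** A criterion that works through a laboratory screen can exclude only what the screen measures. Criterion 8 is written as though the screen covers illicit substances generally and amphetamine in particular. The listed panel does not. A woman using amphetamine or methamphetamine without disclosing it would return a clean result at screening and on Day 0.

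Stimulant use, and coming off a stimulant, can affect mood, sleep and tiredness. Those are the domains that HAMD17, EPDS and the Stanford Sleepiness Scale rate, and HAMD17 carries the primary efficacy endpoint. The same panel is used at the later visits, so use that continued or began during the study would not appear in the urine drug screen summaries either.

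The smaller issue is drafting. Criterion 8 tells the site how to verify a prescribed drug but not how that step relates to 5.3.2 and exclusion 20. A site holding a positive Day 0 result for a prescribed benzodiazepine has one rule that says verify and another that says exclude, with nothing to link them.

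**Working it through.** No rate, power or sample-size formula applies. The check compares the lists and then the timing.

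**1. Drugs named in criterion 8 against the panel**
- Named as examples (4.2): amphetamine, benzodiazepine.
- Panel (Protocol 7.8.5.2): cannabis, opioids, cocaine, benzodiazepines, barbiturates, ethanol, phencyclidine, which is 7 classes.
- Panel (SAP 7.2.2): the same scope, with oxycodone, methadone and buprenorphine named in place of the opioid class.
- Named and tested: benzodiazepine (1 of 2). Named and not tested: amphetamine (1 of 2). Methamphetamine is on neither list.
- Confirmatory testing starts from a result that is already positive, so it adds no analyte. The extra THC assay in criterion 8 concerns cannabis only. The documents describe no other drug screen.

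**2. When the screen is done**
- Urine for the drug screen is listed at screening (7.1) and on Day 0 (7.2).
- The Day 1 pre-infusion lists (7.3.1 for Cohorts 1-5, 7.5.1 for Cohort 6) contain no urine sample. The randomization screen in criterion 8 is therefore the Day 0 sample, taken at admission.
- The drug-free period in 5.3.2 is counted back from admission, so it should already be complete when that sample is taken.

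**3. Prescription classes on the panel against 5.3.2**
- Prescription classes: opioids, benzodiazepines, barbiturates (3). Cocaine, phencyclidine and alcohol are taken here not to be prescription drugs, and cannabis has its own rule.
- Prohibited in 5.3.2 with a drug-free period: 3 of 3.
- Panel classes that verification alone could settle on Day 0 without meeting 5.3.2: 3 - 3 = 0.
- Amphetamine is not listed in 5.3.2. The one named drug that verification could settle without touching 5.3.2 is the one the panel cannot find.

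**4. Leverage of one woman**
- Cohort size 10-30 and 1:1 allocation (Protocol 3.1) give 10/2 = 5 to 30/2 = 15 per arm.
- One woman is 1/15 = 6.7% to 1/5 = 20% of an arm. If her change score were shifted by d points, the arm mean would move by d/15 to d/5. This describes sensitivity and says nothing about how often such use occurs.

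**The case against.** The strongest reply on amphetamine is that it is only an example, so deleting it would make the texts agree, and that other safeguards exist. Exclusion 7 bars any substance use disorder within three years. Section 7.8.4 records all medications over the 60 days before screening. Section 5.3.1.3 sends other medications to the medical monitor before enrolment. These cover diagnosed disorders and disclosed prescriptions. They do not cover undisclosed use without a known disorder, which is what an objective screen is for. Deleting the example would also leave the clause on illicit substances with no means of applying it to stimulants.

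On the prescription check, the reply is stronger and mostly stands. Under 4.2 any single criterion excludes, and exclusion 20 has no prescription exemption. Section 7.2 has the criteria reviewed again on Day 0. Section 7.8.4 already requires start and stop dates for every medication. Criterion 8 says only that legitimate use must be verified; where it means to restore eligibility, in its cannabis sentences, it says so. Verification also has a proper use at screening, when a drug-free period can still follow, and perhaps on Day 0 for a woman who completed that period but still tests positive (the documents give no detection windows).

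A reader might infer that a recent benzodiazepine user with a current pill bottle is cleared for dosing. The documents do not support that, because exclusion 20 would still bar a current user. What remains is a missing cross-reference.

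**Conclusion.** The amphetamine gap holds. One of the two drugs that criterion 8 names is absent from both panel lists, methamphetamine is absent as well, and nothing else in the documents would detect undisclosed use objectively. This assumes that the laboratory runs the listed panel and no more.

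The secondary point holds as an unreconciled link: all three prescription classes on the panel fall under 5.3.2, and criterion 8 does not mention it.

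The number of women affected cannot be derived. A reader might assume a prevalence of, say, 1-3% and conclude that 1-3 of 100 women would be wrongly enrolled, but 100 x 0.01 = 1 and 100 x 0.03 = 3 only restate the assumption. That reading also ignores exclusion 7 and the medication review. Further, 100 is the ceiling for the whole study, and Protocol 1.2.1.4 shows Cohort 1 already dosed and data reviewed for 12 women in Cohort 2 and 13 in Cohort 3. A change now reaches only later enrolments.

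**What to change.** 1. **Panel.** Add amphetamine/methamphetamine to the urine drug screen in Protocol 7.8.5.2 and SAP 7.2.2, on the sample already collected, for women still to be enrolled. In the urine drug screen table, show women enrolled earlier as not tested for this analyte, not as negative.
2. **Criterion 8 (synopsis and 4.2).** Add one sentence stating that verification of legitimate use does not override 5.3.2 or exclusion 20. This makes explicit what the any-one-criterion rule in 4.2 already implies and leaves the drug-free period as it is.
3. **Day 0 positives.** For a class listed in 5.3.2, check the result against the stop date recorded under 7.8.4 before randomization, and document the check. No new data item is needed.

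The cost is a small assay charge, a few more screen failures and short text changes in two documents, with no extra visit or sample.
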